8.1.3. Individual Safety Stopping Criteria

- If a participant experiences a serious or severe clinically significant AE that in the clinical judgement of the Investigator is possibly, probably or definitely related to investigational product.
- The participant becomes pregnant.
- The participant initiates treatment with any prohibited medications.
- The participant develops a serious opportunistic or atypical infection.
- If any of the liver chemistry stopping criteria or QTc stopping criteria are met.
- The participant experiences any signs of suicidal ideation or behaviour.

8.1.4. Temporary Discontinuation

If a participant is not dosed when planned in a particular period (eg, in case of unexpected personal circumstances or AEs that occur between treatment periods), they may be dosed at a later date (if a subject cannot re-attend within 28 days, they should be considered withdrawn), provided the following criteria are met:

- The AE has resolved or stabilised.
- The AE preventing dosing was not considered related to the IMP.
- The participant has not met any individual stopping criteria.
- It is considered safe to continue to dose in the opinion of the investigator.

8.2. Withdrawal from the Study

- A participant may withdraw from the study at any time at his/her own request, or may be withdrawn at any time at the discretion of the investigator for safety, behavioural, compliance or administrative reasons. If a participant withdraws from the study, he/she may request destruction of any samples taken, and the Investigator must document this in the site study records. The reason for withdrawal should be documented in the source data.
- If the participant withdraws consent for disclosure of future information, the sponsor may retain and continue to use any data collected before such a withdrawal of consent.
- The Sponsor's request, for reasons such as significant protocol deviations or participant safety concern (and after discussion with the Investigator).
- If a participant is withdrawn from study treatment, this participant is also considered to be withdrawn from the study following completion of follow-up assessments.
- Study is terminated by the Sponsor.
- Refer to the SoA (Section 2) for data to be collected at the time of study discontinuation and follow-up and for any further evaluations that need to be completed.

8.3. Lost to Follow Up

A participant will be considered lost to follow-up if he or she repeatedly fails to return for scheduled visits and is unable to be contacted by the study site.

The following actions must be taken if a participant fails to return to the clinic for a required study visit:

- The site must attempt to contact the participant and reschedule the missed visit as soon as possible and counsel the participant on the importance of maintaining the assigned visit schedule and ascertain whether or not the participant wishes to and/or should continue in the study.
- Before a participant is deemed lost to follow up, the investigator or designee must make every effort to regain contact with the participant (where possible, 3 telephone calls and, if necessary, a certified letter to the participant's last known mailing address or local equivalent methods). These contact attempts should be documented in the participant's source data.

• Should the participant continue to be unreachable, he/she will be considered to have withdrawn from the study with a primary reason of lost to follow-up.

8.4. Study Stopping Criteria

The study will be halted, and the risk to other participants evaluated, prior to a decision as to whether to terminate the study if any of the following criteria are met:

- A serious adverse reaction (i.e., a serious adverse event considered at least possibly related to the IMP administration) in one subject.
- Severe non-serious adverse reactions (i.e., severe non-serious adverse events considered as, at least possibly related to the IMP administration) in two subjects, independent of within or not within the same system organ class.

Relatedness will be determined by the investigator. If the study is halted, a temporary halt will be submitted to the MHRA and EC in the form of a substantial amendment. The study may be resumed or terminated; however, it will not be resumed until a further substantial amendment to resume the study is submitted and approved by MHRA and EC.

8.5. Study Termination

After the start of protocol activities but prior to the commencement of dosing, the study may be terminated by the sponsor and investigator without consultation with the MHRA and EC. The end of the trial must be notified to the MHRA and EC immediately and at the latest within 15 days after the study is terminated, clearly explaining the reasons. A description of follow up measures taken for safety reasons, if applicable, will also be provided.

If the study is abandoned prior to commencement of any protocol activities, the PI or sponsor must notify the EC and MHRA by letter outlining the reasons for abandonment of the trial.

Once exposure to GSK2982772 has begun, the study will be completed as planned unless the following criteria are satisfied that require a temporary halt or early termination of the study.

- The occurrence of serious or severe AE(s), as defined in Appendix 4, if considered to be related to the IMP.
- New information regarding the safety of the IMP that indicates a change in the risk/benefit profile for the compound, such that the risk/benefit is no longer acceptable for participants in the study.
- Significant violation of Good Clinical Practice (GCP) that compromises the ability to achieve the primary study objectives or compromises participant safety.

If any of the above occurs, the study will be terminated if careful review of the overall risk/benefit analysis described in Section 3.3 demonstrates that the assumptions have changed and that the overall balance is no longer acceptable. In these circumstances,

termination can only take place with the agreement of the investigator and sponsor. The MHRA and EC will be informed of study termination.

If it becomes necessary to consider termination of the study after dosing has begun, dosing may be suspended pending discussion between the investigator and sponsor. Dosing will be stopped immediately on safety grounds.

The study may be terminated or suspended at the request of the MHRA or EC.

9. STUDY ASSESSMENTS AND PROCEDURES

- Study procedures and their timing are summarised in the SoA (Section 2).
- Protocol waivers or exemptions are not allowed.
- Immediate safety concerns should be discussed with the sponsor immediately upon occurrence or awareness to determine if the participant should continue or discontinue study treatment.
- Adherence to the study design requirements, including those specified in the SoA (Section 2), is essential and required for study conduct.
- All screening evaluations must be completed and reviewed to confirm that potential participants meet all eligibility criteria. The investigator will maintain a screening log to record details of all participants screened and to confirm eligibility or record reasons for screening failure, as applicable.
- Procedures conducted as part of the participant's routine clinical management or by generic screening (eg, blood count) and obtained before signing of ICF may be utilised for screening or baseline purposes provided the procedure met the protocol-specified criteria and was performed within the time frame defined in the SoA (Section 2).
- The maximum amount of blood collected from each participant over the duration of the study, including any extra assessments that may be required, will not exceed 550 mL in a 70-day period.
- Repeat or unscheduled samples may be taken for safety reasons or for technical issues with the samples.
- A participant will be allowed to leave the premises following completion of study-specific procedures at 48 hours post-dose (Part A, Treatment Periods 1, 3, 4, 5, 6 and Part B, all periods) or 24 hours post-dose (Part A, Treatment Period 2) providing that:
 - No AEs have been reported during the study visit
 - The participant responds positively when asked "How are you feeling?"

If any of these conditions are not met, then the participant may only be allowed to leave the clinical unit with the authorisation of the investigator or appropriately qualified delegate.

9.1. Efficacy Assessments

Not applicable.

9.2. Adverse Events

The definitions of an AE or SAE can be found in Appendix 4.

The investigator and any designees are responsible for detecting, documenting, and reporting events that meet the definition of an AE or SAE and remain responsible for following up AEs that are serious, considered related to the study treatment or the study, or that caused the participant to discontinue the study treatment (see Section 8).

9.2.1. Time Period and Frequency for Collecting AE and SAE Information

- All SAEs will be collected from the signing of the ICF until the follow-up visit at the time points specified in the SoA (Section 2).
- All AEs will be collected from the start of treatment until the follow-up visit at the time points specified in the SoA (Section 2).
- Medical occurrences that begin before the start of study treatment but after obtaining informed consent will be recorded on the Medical History/Current Medical Conditions section of the source data not the AE section.
- All SAEs will be recorded and reported to the sponsor or designee within 24 hours, as indicated in Appendix 4. The investigator will submit any updated SAE data to the sponsor within 24 hours of it being available.
- Investigators are not obligated to actively seek AEs or SAEs in former study participants. However, if the investigator learns of any SAE, including a death, at any time after a participant has been discharged from the study, and he/she considers the event to be reasonably related to the study treatment or study participation, the investigator must promptly notify the sponsor.
- The method of recording, evaluating, and assessing causality of AEs and SAEs and the procedures for completing and transmitting SAE reports are provided in Appendix 4.

9.2.2. Method of Detecting AEs and SAEs

Care will be taken not to introduce bias when detecting AE and/or SAE. Open-ended and non-leading verbal questioning of the participant is the preferred method to inquire about AE occurrence.

9.2.3. Follow-up of AEs and SAEs

After the initial AE/SAE report, the investigator is required to proactively follow each participant at subsequent visits/contacts. All SAEs will be followed until the event is resolved, stabilised, otherwise explained, or the participant is lost to follow-up (as

defined in Section 8.3). Further information on follow-up procedures is given in Appendix 4.

9.2.4. Regulatory Reporting Requirements for SAEs

- Prompt notification by the investigator to the sponsor of a SAE is essential so that legal obligations and ethical responsibilities towards the safety of participants and the safety of a study treatment under clinical investigation are met.
- The sponsor has a legal responsibility to notify both the local regulatory authority and other regulatory agencies about the safety of a study treatment under clinical investigation. The sponsor will comply with country-specific regulatory requirements relating to safety reporting to the regulatory authority, Institutional Review Boards (IRB)/Independent Ethics Committees (IEC), and investigators.
- Investigator safety reports must be prepared for SUSARs according to local regulatory requirements and sponsor policy and forwarded to investigators as necessary.
- An investigator who receives an investigator safety report describing a SAE or other specific safety information e.g., summary or listing of SAE) from the sponsor will review and then file it along with the Investigator's Brochure and will notify the IRB/IEC, if appropriate according to local requirements.
- Further details can be found in Appendix 7.

9.2.5. Pregnancy

- Details of all pregnancies in female participants and, female partners of male participants will be collected after the start of study treatment and until the follow-up visit at the time points specified in the SoA (Section 2).
- If a pregnancy is reported, the investigator should inform GSK within 24 hours of learning of the pregnancy and should follow the procedures outlined in Appendix 5.
- Abnormal pregnancy outcomes (e.g., spontaneous abortion, foetal death, stillbirth, congenital anomalies, ectopic pregnancy) are considered SAE.

9.3. Treatment of Overdose

For this study, any dose of GSK2982772 greater than that intended in this study will be considered an overdose.

There is no specific antidote for overdose with GSK2982772.

In the event of an overdose, the investigator should:

1. Contact the Medical Monitor immediately.

- 2. Closely monitor the participant for AE/SAE and laboratory abnormalities until study treatment can no longer be detected systemically (at least 48 hours following the last dose of GSK2982772).
- 3. Obtain a plasma sample for PK analysis if requested by the Medical Monitor (determined on a case-by-case basis).
- 4. Document the quantity of the excess dose as well as the duration of the overdosing in the source.

Decisions regarding dose interruptions or modifications will be made by the investigator in consultation with the Medical Monitor based on the clinical evaluation of the participant.

9.4. Safety Assessments

Planned time points for all safety assessments are provided in the SoA (Section 2).

9.4.1. Physical Examinations

- A complete physical examination will include, at a minimum, assessments of the skin, cardiovascular, respiratory, GI and neurological systems. Height and weight will also be measured and recorded.
- A brief physical examination will include, at a minimum, assessments of the skin, lungs, cardiovascular system, and abdomen (liver and spleen).
- Investigators should pay special attention to clinical signs related to previous serious illnesses.

9.4.2. Vital Signs

- Vital signs will be measured in a semi-supine position after 5 minutes rest and will include temperature, systolic and diastolic blood pressure, heart rate and respiratory rate.
- The acceptable deviations from the nominal vital signs measurement time points are:
 - The pre-dose vital signs measurements will be taken ≤2 hours before dosing.
 - Post-dose vital signs measurements will be taken ± 15 minutes from the nominal post-dose time points.
 - Discharge vital signs measurements will be taken ± 1 hour from the nominal time point.
- If a participant shows an abnormal assessment at any stage, repeat measurements may be made and the abnormality followed to resolution if required. Additional measurements may be taken as deemed necessary by the investigator.
- Any clinically significant abnormality, including changes from baseline (pre-dose Day 1), must be reported as an AE.

9.4.3. Electrocardiograms

- Triplicate 12-lead ECGs will be obtained at screening and single 12-lead ECGs will be obtained as outlined in the SoA (Section 2) using an ECG machine that automatically calculates the heart rate and measures PR, QRS, QT, and QTc intervals. If a single ECG shows a QTc increase of ≥60 msec from baseline (pre-dose Day 1), two further ECGs should be performed over a brief period (eg, 5 to 10 minutes) and the assessment made on the mean QTc of the triplicate ECGs. Refer to Section 8.1.2 for QTc withdrawal criteria and additional QTc readings that may be necessary.
- The QTc should be based on averaged QTc values of triplicate ECGs obtained over a brief (eg, 5 to 10 minutes) recording period.
- The acceptable deviations from the nominal ECG measurement time points are:
 - The pre-dose ECG measurements will be taken ≤ 2 hours before dosing
 - Post-dose ECG measurements will be taken ± 15 minutes from the nominal post-dose time point.
 - Discharge ECG measurements will be taken ± 1 hour from the nominal time point.
- ECGs are to be measured after participant has been in a semi-supine or supine position after approximately 5 minutes rest.
- If a participant shows an abnormal assessment at any stage, repeat measurements may be made and the abnormality followed to resolution if required. Additional measurements may be taken as deemed necessary by the investigator.
- Any clinically significant abnormality, including changes from baseline (pre-dose Day 1), will be reported as an AE.

9.4.4. Clinical Safety Laboratory Assessments

- Refer to Appendix 2 for the list of clinical laboratory tests to be performed and to the SoA (Section 2) for the timing and frequency.
- Blood samples for scheduled laboratory assessments will be taken following an overnight fast.
- The acceptable deviations from the nominal blood sampling time points for laboratory assessments are:
 - Post-dose blood samples will be taken ± 1 hour from the nominal blood sampling time except when the time point coincides with the PK blood sampling time. In this situation, the time window for the PK sample applies.
- The acceptable deviations from the nominal urine sampling time points for urinalysis are:
 - Post-dose urine samples will be taken ± 2 hour from the nominal urine sampling time.

- The investigator must review the laboratory report, document this review, and record any clinically relevant changes occurring during the study in the AE section of the study database. The laboratory reports must be filed with the source documents. Clinically significant abnormal laboratory findings are those that are not associated with the underlying disease, unless judged by the investigator to be more severe than expected for the participant's condition.
- All laboratory tests with values considered clinically significantly abnormal during participation in the study or within 7 days after the last dose of study treatment should be repeated until the values return to normal or baseline or are no longer considered significantly abnormal by the investigator or medical monitor.
- If such values do not return to normal/baseline within a period of time judged reasonable by the investigator, the etiology should be identified and the sponsor notified.
- All protocol-required laboratory assessments, as defined in Appendix 2, must be conducted in accordance with the laboratory manual and the SoA (Section 2).
- If laboratory values from non-protocol specified laboratory assessments performed at the institution's local laboratory require a change in participant management or are considered clinically significant by the investigator (eg, SAE or AE or dose modification), then the results must be recorded in the source.

9.4.5. Suicidal Risk Monitoring

GSK2982772 is considered to be a CNS-active drug. There has been some concern that some CNS-active drugs may be associated with an increased risk of suicidal thinking or behaviour when given to some patients with disease. Although this drug has not been shown to be associated with an increased risk of suicidal thinking or behaviour when given to healthy volunteers, GSK considers it important to monitor for such events before or during clinical studies with compounds such as this.

Participants being treated with GSK2982772 should be monitored appropriately for suicidal ideation and behaviour or any other unusual changes in behaviour. Study medication must be immediately discontinued in all participants who experience signs of suicidal ideation or behaviour.

Families and caregivers of patients being treated with GSK2982772 should be alerted about the need to monitor participants for the emergence of unusual changes in behaviour, as well as the emergence of suicidal ideation and behaviour and to report such symptoms immediately to the study Investigator.

9.5. Pharmacokinetics

• Blood samples of approximately 2 mL will be collected for measurement of plasma concentrations of GSK2982772 as specified in the SoA (see Section 2). Instructions for the collection and handling of biological samples will be provided by the sponsor. The actual date and time (24-hour clock time) of each sample will be recorded.

- Processing, storage and shipping procedures are provided in the Study Reference Manual (SRM) or equivalent.
- The acceptable deviations from the nominal post-dose blood sampling times are as follows:
 - The pre-dose blood sample will be taken ≤ 1 hour before dosing.
 - Post-dose samples will be taken within ± 10 minutes of the nominal post-dose sampling time
- Samples will be used to evaluate the PK of GSK2982772. Samples collected for analyses of GSK2982772 plasma concentration may also be used to evaluate safety aspects related to concerns arising during or after the study.
- Genetic analyses will not be performed on these plasma samples. Participant confidentiality will be maintained.

Plasma analysis will be performed under the control of Platform Technology & Science (PTS), In Vitro/In Vivo Translation (IVIVT) and Third Party Resourcing (TPR), GSK. Concentrations of GSK2982772 will be determined in plasma using the current approved bioanalytical methodology. Raw data will be archived at the Bioanalytical site as detailed in the SRM or equivalent.

9.6. Pharmacodynamics

Pharmacodynamic parameters are not evaluated in this study.

9.7. Genetics

- A 6 mL blood sample for DNA isolation will be collected from participants who have consented to participate in the genetics analysis component of the study, as specified in the SoA (see Section 2). Participation is optional. Participants who do not wish to participate in the genetic research may still participate in the study.
- In the event of DNA extraction failure, a replacement genetic blood sample may be requested from the participant. Signed informed consent will be required to obtain a replacement sample unless it was included in the original consent.
- See Appendix 8 for information regarding genetic research. Details on processes for collection and shipment and destruction of these samples can be found in the SRM or equivalent.

9.8. Biomarkers

Biomarkers are not evaluated in this study.

9.9. Health Economics OR Medical Resource Utilization and Health Economics

Health Economics/Medical Resource Utilization and Health Economics parameters are not evaluated in this study.

10. STATISTICAL CONSIDERATIONS

10.1. Hypotheses

No formal hypothesis will be tested. However, point estimates and corresponding 90% confidence intervals will be derived for C_{max} , $AUC_{(0-24)}$, $AUC_{(0-inf)}$ and C_{24h} .

10.2. Sample Size Determination

The maximum between-subject coefficient of variation (CV_b) for the PK parameters observed in Part A of Study 205017 were used for precision estimates; CV_b (%) for AUC_(0-inf), C_{max}, C_{18h}, C_{20h}, C_{22h}, and C_{24h} were 48.7%, 58.5%, 68.5%, 68.7%, 65.1%, and 73.2%, respectively. Therefore, the respective estimates of within subject coefficient of variation (CV_w [%]) are 30.9%, 36.7%, 42.3%, 42.5%, 40.4%, and 44.9%. Based on these estimates of variability and a sample size of 12 completers, it is estimated that the lower and upper bounds of the 90% confidence interval (CI) for the geometric mean ratio (MR/IR) of AUC and C_{max} will be within approximately 24.3% and 29.2% of the point estimate, respectively. Similarly, it is estimated that the lower and upper bounds of the geometric mean ratio (MR2/MR1) of C_{18h}, C_{20h}, C_{22h}, and C_{24h} will be within approximately 32.3%, 33.9%, 34.1%, and 36.2% of the point estimate, respectively.

Since it is expected that the MR1 tablet formulation vs IR is to reduce C_{max} by 80% and AUC by 40%, a sample size of 12 ensures that the 90% CI is within the region 0.459-0.796 for AUC and 0.132-0.310 for C_{max} if the observed geometric ratio is 0.57-0.64 for AUC and 0.17-0.24 for C_{max} . Since it is expected that the MR2 tablet formulation will increase C_{18h} , C_{20h} , C_{22h} , and C_{24h} by 28%, 43%, 44%, and 27%, respectively vs MR1, a sample size of 12 ensures that the 90% CI is within the region 0.945-1.746 for C_{18h} , 1.046-1.968 for C_{20h} , 1.051-1.985 for C_{22h} , and 0.910-1.784 for C_{24h} if the observed geometric mean ratio is 1.25-1.32 for C_{18h} , 1.40-1.47 for C_{20h} , 1.41-1.48 for C_{22h} , and 1.24-1.31 for C_{24h} .

Sample Size Sensitivity

Using estimates of parameter (this can be any PK parameter AUC, C_{max}) variability observed in Part A of Study 205017, the precision of these estimates calculated as half width of a 90% confidence interval for the mean ratio (MR/IR or MR2/MR1) and expressed as distance from mean to limits for 10, 12, 14 and 16 participants has been calculated (Table 3).

Parameter	CVw (%)	Precision of Mean Ratio (%)				
		N=10	N=12	N=14	N=16	
AUC	30.9	27.5	24.3	22.0	20.3	
C _{max}	36.7	33.1	29.2	26.4	24.3	
C _{18h}	42.3	36.7	32.3	29.2	26.8	
C _{20h}	42.5	38.6	33.9	30.6	28.1	
C _{22h}	40.4	38.8	34.1	30.8	28.3	
C _{24h}	44.9	41.1	36.2	32.6	29.9	

Table 3 Precision Estimate of Mean Ratio

For example, based upon the estimate of variability ($CV_w\%$) of 30.9 and a sample size of 16, it is estimated that the lower and upper bounds of the 90% confidence interval for the geometric mean ratio of the PK parameter (eg, AUC, C_{max}) will be within approximately 20.3% of the point estimate.

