10.4. Statistical Analyses

10.4.1. Pharmacokinetic Analyses

All PK analyses will be performed on the PK Population.

For both parts of the study, plasma GSK2982772 concentration-time data will be analysed by non-compartmental methods.

The plasma concentration-time data for each of the regimens, the following PK parameters will be determined, as data permit:

- maximum observed plasma concentration (C_{max}).
- time to C_{max} (T_{max}).
- the elapsed time from dosing at which GSK2982772 was first quantifiable in a concentration vs time profile (T_{lag}).
- observed concentration at 24 hours post-dose (C_{24h}).
- observed concentration at 8 and 12 hours post-dose (C_{8h} and C_{12h}) for IR only.
- area under the plasma concentration vs time curve (AUC_(0-t), AUC₍₀₋₂₄₎ and AUC_(0-inf)).
- the percentage of AUC extrapolated beyond the last measured time point (AUC%extrap).
- terminal half-life $(t_{1/2})$.
- relative bioavailability (Frel_{formulation}) of test formulations (under fed or fasted conditions) vs reference formulation based on AUC₍₀₋₂₄₎ and AUC_(0-inf) (or AUC_(0-t) if AUC_(0-inf) can't be derived) and C_{max}.
- relative bioavailability (Frel_{FE}) of fed (high-fat breakfast or high-fat evening meal, standard breakfast or standard evening meal or delayed meal (30 or 60 minutes) vs fasted based on AUC and C_{max}.
- relative bioavailability (Frel(time effect) of evening dosing vs morning dosing based on AUC and C_{max})
- relative bioavailability (Frel_{MRFormulation}) of MR prototype coated tablet formulations relative to each other, as appropriate, based on AUC and C_{max} (optional Part B only)
- C_{max}/Dose and AUC/Dose (optional Part B only)

Descriptive statistics (n, arithmetic mean, standard deviation [SD], 95% CI, minimum, median and maximum) will be calculated by treatment for all PK concentrations over time and for the derived PK parameters. In addition, for log_e-transformed PK parameter variables geometric mean, 95% CI and %CV_b (100 * $\sqrt{(exp(SD2) - 1)}$) will be provided, where the SD is the standard deviation of log-transformed data.

Endpoint	Statistical Analysis Methods
Primary	The primary PK endpoints to compare MR formulations with IR formulations will be summarised descriptively. Ratios of $AUC_{(0-inf)}$, $AUC_{(0-24)}$, $(AUC_{(0-t)}$, if $AUC_{(0-inf)}$ cannot be derived), C_{max} , C_{24h} for MR formulation to IR formulation will be computed with 90% CI.

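### Protocol 10.2 treats its 90% CI regions as guaranteed by 12 completers, but at the ends of the stated ratio ranges the AUC, Cmax and C24h intervals stay inside only about half to three quarters of the time

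*Protocol*

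**What the plan says.** Section 10.1 of the protocol sets an estimation aim: "No formal hypothesis will be tested. However, point estimates and corresponding 90% confidence intervals will be derived for" the main PK parameters. Section 10.2 supports 12 completers by precision. It starts from Study 205017: "The maximum between-subject coefficient of variation" values for AUC, Cmax, C18h, C20h, C22h and C24h "were 48.7%, 58.5%, 68.5%, 68.7%, 65.1%, and 73.2%, respectively". It goes on: "Therefore, the respective estimates of within subject coefficient of variation" "are 30.9%, 36.7%, 42.3%, 42.5%, 40.4%, and 44.9"%. No ratio, correlation or source is given for that step.

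"Based on these estimates of variability and a sample size of 12 completers", it gives half-widths of 24.3% (AUC), 29.2% (Cmax), 32.3% (C18h), 33.9% (C20h), 34.1% (C22h) and 36.2% (C24h). The next paragraph states that "a sample size of 12 ensures that the 90% CI is within the region 0.459-0.796 for AUC" if the observed ratio is 0.57-0.64, with matching statements for the other five parameters. Table 3 repeats the half-widths for N = 10, 12, 14 and 16, with one CVw per parameter.

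**The concern.** A confidence interval for a geometric mean ratio has a random centre and a random width. The sentence fixes the centre by conditioning on the observed ratio, but says nothing about the width, which scales with the observed residual SD. If the region leaves no slack beyond the planned width, any observed SD above plan breaks it. A guarantee is then the wrong description.

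Section 10.2 is the only quantitative support for 12 evaluable participants, a number that Section 5.1.3 reuses for interim decisions. Someone relying on it would think the precision firmer than it is. The printed half-widths for C18h, C20h and C22h also rise while the CVw for C22h falls, which suggests a row error in the time window that Section 5.1.3 uses for formulation selection.

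**Working it through.** **Inputs.** n = 12; two-sided 90% interval; CVw, half-widths, ratio ranges and regions from Section 10.2. The error df are my derivation. A paired comparison of two regimens in 12 completers has 11. The mixed model in SAP 8.1.5.1, with up to six observations per participant, has 12×6 − 12 − 5 = 55.

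**1. Reproduce the regions.** Region = low ratio ÷ (1 + w) to high ratio × (1 + w), where w is the stated half-width. AUC: 0.57 ÷ 1.243 = 0.459 and 0.64 × 1.243 = 0.796. These match, and the other five regions follow the same rule. At each range end the nearer bound is therefore exactly one planned half-width away.

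**2. Reproduce the half-widths.** σ² = ln(1 + CVw²); w = exp(t × √(2σ²/12)) − 1. For AUC, σ² = ln(1 + 0.309²) = 0.0912 and √(2 × 0.0912/12) = 0.1233. With 11 df (t = 1.796) w = 24.8%; with 14 df (t = 1.761) w = 24.3%, the printed value. At 11 df Cmax gives 29.8% (stated 29.2%) and C24h 36.9% (36.2%).

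**3. Chance that the interval stays inside.** For lognormal data the residual variance is independent of the estimated ratio. Given an observed ratio g, the interval lies in (L, U) if s² ≤ s²max = 6 × [min(ln(g/L), ln(U/g))/t]². The probability is P(χ²_df ≤ df × s²max/σ²). For AUC at g = 0.57 with 11 df: ln(0.57/0.459) = 0.2166; s²max = 6 × (0.2166/1.796)² = 0.0873; 11 × 0.0873/0.0912 = 10.53; probability 0.52. With the planned CVw taken as true:

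| Parameter | Range ends, 11 df | Range ends, 55 df | Expected ratio, 11 to 55 df |
|---|---|---|---|
| AUC | 0.52, 0.53 | 0.72, 0.75 | 0.86 to over 0.99 (ratio 0.60) |
| Cmax | 0.50, 0.52 | 0.69, 0.73 | about 1.0 (0.20) |
| C24h | 0.53, 0.53 | 0.74, 0.74 | 0.66 to 0.93 (1.27) |
| C20h, as printed | 0.51, 0.51 | 0.71, 0.71 | 0.64 to 0.91 (1.43) |
| C18h, as printed | 0.44, 0.44 | 0.56, 0.56 | 0.59 to 0.85 (1.28) |
| C22h, as printed | 0.61, 0.61 | 0.88, 0.88 | 0.73 to 0.97 (1.44) |

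**4. Why C18h and C22h differ.** With 14 df, the CVw values printed for C18h, C20h and C22h (42.3, 42.5, 40.4%) give half-widths of 33.9, 34.0 and 32.3%. The printed half-widths are 32.3, 33.9 and 34.1%. Taking CVw as 40.4, 42.3 and 42.5% gives 32.3, 33.9 and 34.0%. The same shift fits the N = 10, 14 and 16 columns of Table 3. With that matching, the range-end chances for the three parameters run from about 0.52 to 0.74, in line with the others.

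**5. Half-width met with 80% probability.** Multiply the log half-width by √(χ²₀.₈/df). At 11 df this is √(14.63/11) = 1.153. AUC: exp(0.2214 × 1.153) − 1 = 29.1%. Likewise Cmax is 35.1% and C24h 43.7%, against 24.3, 29.2 and 36.2% stated.

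**6. Where CVw comes from.** ln(1 + CVw²)/ln(1 + CVb²) = 0.4285, 0.4293, 0.4278, 0.4295, 0.4279, 0.4280. A single factor of 3/7 = 0.4286 returns all six printed CVw values to one decimal. Applied to the AUC CVb of 48.7%, factors of 0.3, 0.5 and 0.7 give CVw of 25.7, 33.5 and 40.1%, and half-widths at N = 12 (11 df) of 20.4, 27.0 and 32.7%.

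**The case against.** The range ends are the worst case. About one half at 11 df is built in there, because the region equals the planned interval. At the expected AUC and Cmax ratios the slack is real. The plan started from the maximum CVb in Study 205017, a cautious choice, so true coverage may be better. The half-width sentences are properly hedged; only the region sentence is not. Up to 16 participants are enrolled. If all six regimens are pooled (55 df), the 80% half-widths are 24.8, 29.8 and 37.0%, close to those stated. No decision uses the regions: selection rests on the 18-24 h concentrations and their variability, stopping on visual judgement (Section 10.4.4), and Section 5.1.3 allows decisions on fewer than 12. All of this stands and limits the impact. None of it makes the region sentence true as written.

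Three stronger readings are tempting. One is that the 3/7 factor causes the shortfall. It does not: step 3 takes the planned CVw as correct. A second is that CVw is wrong because CVb already contains within-subject variance, so that a 30% share would give 25.7% for AUC. The formula in Section 10.4.1, "where the SD is the standard deviation of log-transformed data", defines this study's summaries. The documents do not say how the CVb in Study 205017 was obtained, and no 30:70 split appears in them. On that reading N = 12 would be more precise than stated, with AUC range-end chances of 0.82-0.83 at 11 df. With a factor of 0.5 they would fall to 0.38-0.39. The documents support neither direction. A third is that 12 completers are too few; with no hypothesis and no precision target, nothing here shows that.

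**Conclusion.** The guarantee in Section 10.2 does not hold. If the planned CVw is true, the interval stays in its region at the range ends about 52-75% of the time for AUC, 50-73% for Cmax and 53-74% for C24h, depending on whether 11 or 55 error df apply. It does better inside the ranges, though C24h reaches only 0.66-0.93 at its expected ratio. The C18h, C20h and C22h half-widths and CVw values are mismatched as printed. The documents do not show which column is wrong, or whether the CVb values share the error.

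The undeclared 3/7 conversion is a separate and secondary matter of disclosure: the documents do not show whether it over- or understates the true CVw. The figures assume lognormal data, a common residual variance and 12 complete participants. The consequence is modest: a claim about precision is overstated, but no test, estimate or decision rule changes.

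**What to change.** Leave N unchanged and amend Section 10.2:

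- Replace *ensures* with *is expected to give, if the observed CVw does not exceed the planned value*.
- Beside each stated half-width, give the one met with 80% probability, and state the df. At 11 df: AUC 29.1%, Cmax 35.1%, C24h 43.7%.
- Extend Table 3 to vary CVw as well as N.
- Check the C18h, C20h and C22h rows against the source output. Realign the CVw values or the half-widths in the text and Table 3, and recompute the regions if the half-widths move.
- State that CVw was obtained as 3/7 of the CVb log-variance, give the source, label it as an assumption, and say what CVb measured in Study 205017.

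The cost is a few sentences and a small table. The 80% half-widths will look less favourable than the present figures. Design, conduct and analysis are unaffected.
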